**▪ Objective:**

- Effectiveness of the proposed VVCS disc (approx. disc diameter 7.1 mm) to provide temporary hemostasis in presence of an adjacent sheath
- Disc deployment integrity in presence of an adjacent sheath

**▪ Abbreviated High-level Results Summary:**

- 8 cases were performed
- Average ACT 356 sec. Animals were treated with ASA and Plavix 3 days prior to the study
- Dual access with a 12F sheath and either a 7 or 8F accompanying sheath
- Access separation measured from 2 to 6 mm at vessel level
- All cases showed temporary hemostasis with the disc in presence of a neighboring sheath, as was evident by venograms and lack of any extravasation in surrounding tissue

▪ **Conclusion:** The study shows that Mid-Bore VVCS disc can be deployed, de-deployed and removed in presence of another indwelling sheath and perform satisfactorily.

#### **1.4. Clinical Studies**

##### **RESPECT Trial using VASCADE arterial VCS**

VASCADE 6/7F VCS was evaluated in a prospective, multi-center, randomized (2:1) clinical trial (the RESPECT Trial) in 20 sites in the United States and one site in Australia, comparing VASCADE VCS to Manual Compression (MC). The trial involved 420 patients undergoing diagnostic ( $n = 211$ ) or interventional ( $n = 209$ ) endovascular procedures, with 275 of those subjects receiving the VACADE device.

The RESPECT trial was designed to evaluate the safety and effectiveness of the VASCADE 6/7 Fr VCS in sealing femoral arterial access sites. It was specifically designed to demonstrate a reduction in hemostasis, ambulation, and eligibility for hospital discharge in comparison to manual compression.

**Table 1** and **Table 2** summarize safety and efficacy data from the RESPECT study.

Since commercial release in 2013, real-world experience with over 124,000 devices sold in the US, the data indicates the ongoing relevance of the clinical trial results (Tables 1, 2):

- 0.36% Reported Complaint Rate
- 0.1% Reported Patient Complication Rate

The VASCADE VCS platform has an established safety track record in controlled clinical settings and real world usage. VASCADE VCS's safety profile has been established in arterial vessel closure, which generally provides a more difficult closure environment compared to venous closure due to higher blood pressure.

**Table 1: Access Site-Related Complications at 30 Days by Event**

	Total (N=417)				
	VASCADE (N=275)	Manual Compression (N=142)		p-value*	
Any Access Site-Related Major Complication	0	0.0%	0	0.0%	1.00
Access site-related bleeding requiring transfusion	0	0.0%	0	0.0%	1.00
Vascular injury requiring repair	0	0.0%	0	0.0%	1.00
New ipsilateral lower extremity ischemia causing a threat to the viability of the limb	0	0.0%	0	0.0%	1.00
Access site-related infection requiring intravenous antibiotics and/or extended hospitalization	0	0.0%	0	0.0%	1.00
New onset access site-related neuropathy in the ipsilateral lower extremity requiring surgical repair	0	0.0%	0	0.0%	1.00
Permanent access site-related nerve injury (> 30 days)	0	0.0%	0	0.0%	1.00
Any Access Site-Related Minor Complication	3	1.1%	10	7.0%	0.002
Access site-related bleeding requiring > 30 minutes to achieve hemostasis	1	0.4%	10	7.0%	0.0001
Access site-related hematoma > 6 cm	1	0.4%	0	0%	1.00
Late access site-related bleeding (following hospital discharge)	0	0%	0	0%	1.00
Ipsilateral lower extremity arterial emboli	0	0%	0	0%	1.00
Ipsilateral deep vein thrombosis**	4	1.5%	0	0%	NA
Access site-related vessel laceration	0	0%	0	0%	1.00
Access site wound dehiscence	0	0%	0	0%	1.00
Localized access site infection treated with intramuscular or oral antibiotics	0	0%	0	0%	1.00
Arteriovenous fistula not requiring treatment**	1	0.4%	0	0%	NA
Pseudoaneurysm requiring thrombin injection or fibrin adhesive injection**	1	0.4%	0	0%	NA
Pseudoaneurysm not requiring treatment**	4	1.5%	0	0%	NA
New onset access site-related neuropathy in the ipsilateral lower extremity not requiring surgical repair	1	0.4%	0	0%	1.00
Ipsilateral pedal pulse diminished by two grades or transiently lost	0	0%	0	0%	1.00

\*Two-sided Fisher's exact test

\*\*Due to different complication-detecting methods between study arms (100 VASCADE patients and no other study patients underwent a femoral ultrasound exam in an ultrasound sub-study), rates for pseudoaneurysm requiring or not requiring treatment, arteriovenous fistula not requiring treatment, and ipsilateral deep vein thrombosis (which were detected by ultrasound exam) are presented but not compared between arms, nor are they included in the computation of the VASCADE overall minor complication rate (top row).

**Table 2: RESPECT Efficacy Endpoint Results**

	Total N=420	VASCADE (N=278)	Manual Compression (N=142)	p-value*
Time to Hemostasis (minutes)				
N	275	142		
Mean	4.8	21.4		< 0.0001
Std Deviation	5.4	12.4		
Median	3.0	20.0		< 0.0001
Min	0.6	0.0		
Max	31.6	97.0		
Time to Ambulation (hours)				
N	275	142		
Mean	3.8	5.8		< 0.0001
Std Deviation	5.1	3.1		
Median	3.2	5.2		< 0.0001
Min	1.0	1.7		
Max	78.0	22.8		
Time to Discharge Eligibility (hours)				
N	274	142		
Mean	4.8	6.5		0.001
Std Deviation	6.4	3.3		
Median	3.6	5.7		< 0.0001
Min	1.4	2.2		
Max	78.4	23.2		
Time to Hospital Discharge (hours)				
N	275	142		
Mean	18.3	13.7		0.04
Std Deviation	34.5	9.8		
Median	17.2	13.9		0.94
Min	1.7	2.4		
Max	432.9	55.6		
*p-value from t-test for comparing means and Wilcoxon's test for comparing medians				

## **1.5. Risks and Benefits**

### **1.5.1. Risks**

Risks associated with the Cardiva Mid-Bore VVCS are similar to those associated with other extravascular methods of achieving hemostasis at venotomy sites. Complications that may occur include:

- Allergic response
- Arterio-venous fistula
- Bleeding/oozing from the puncture site
- Bruising at puncture site
- Death
- Deep vein thrombosis
- Device failure / malfunction
- Edema
- Embolization (thrombus, air, calcific debris, device)
- Hematoma
- Infection
- Inflammatory response
- Intimal tear / dissection
- Laceration of the vessel wall
- Lower extremity ischemia
- Peripheral nerve injury
- Perforation of the vessel wall
- Pseudoaneurysm
- Pulmonary embolism
- Puncture site pain
- Retroperitoneal bleeding
- Vasovagal response
- Vascular injury
- Vessel occlusion
- Vessel thrombus
- Wound dehiscence

### **1.5.2. Benefits**

The potential benefits of the Cardiva Mid-Bore VVCS over manual compression alone to achieve venous hemostasis include reduced time to ambulation, which the trial is intended to evaluate, in combination with a safety profile that is at minimum non-inferior to manual compression.

### **1.6. Rationale for Ultrasound Sub-study**

A sub-study of this pivotal U.S. clinical trial will be performed utilizing independent analysis of non-invasive duplex ultrasound (DUS) imaging in 25 subjects from each pivotal cohort (i.e., right and left femoral venous access sites, constituting 2 exams per subject), who were randomized to and received the assigned treatment. DUS evaluation will be utilized to assess the local vascular impact of the Cardiva Mid-Bore VVCS or manual compression, along with the development of iatrogenic vascular complications. Specific investigational sites will be designated as ultrasound sites. These 3 – 4 sites will include subjects in the ultrasound sub-study imaging until a total of 25 patients have been evaluated in each treatment arm. Ultrasound will be performed at the follow-up office visit. All sub-study sites will be instructed in performance of duplex ultrasonography of the femoral vascular structures, and images will be interpreted by a central core ultrasound laboratory with experience in multicenter vascular device trials.

## **2. Device Description**

[figure not shown]
The Cardiva Mid-Bore Venous Vascular Closure System (VVCS) is indicated for the percutaneous closure of femoral venous access sites while reducing times to ambulation and discharge eligibility in patients who have undergone catheter-based procedures utilizing 6 – 12 Fr procedural sheaths, with single or multiple access sites per limb, ranging from a single access site in one limb to multiple access sites in both limbs.

The Cardiva Mid-Bore VVCS is a disposable device based on the previously approved VASCADE 6/7F arterial VCS device. The only significant change with respect to the approved device is an increase in disc diameter from ~19F to ~21F to ensure temporary hemostasis and proper collagen deployment during closure of larger bore holes.

As in the previously approved device, the Mid-Bore VVCS device is designed to deliver a resorbable collagen patch extravascularly to block blood flow from the femoral venotomy site at the completion of a catheterization procedure. Cardiva's Mid-Bore VVCS devices are intended to assist physicians or catheter lab technicians in controlling bleeding from femoral venotomy sites and reduce time to ambulation.

The Mid-Bore VVCS device is used in conjunction with 6 – 12 Fr inner diameter introducer sheaths. The VVCS device is introduced through a compatible procedure sheath at the completion of a catheterization procedure.

The Mid-Bore VVCS is comprised of a catheter containing a resorbable collagen implant. Refer to Figure 1 below for an image of the device.

**Figure 1: Cardiva Mid-Bore VVCS with Disc Deployed**

To use the Cardiva VVCS, the catheter is inserted into the femoral vein through the previously placed introducer sheath. After insertion, the distal tip of the catheter is deployed, opening and expanding a low-profile Nitinol (NiTi) disc within the lumen of the femoral vein. The introducer sheath is then removed from the vessel over the catheter and the low-profile disc is placed against the inner wall, locating the vessel wall and temporarily sealing the venotomy. The position of the device disc against the vessel wall locates the collagen patch in the tissue tract immediately adjacent to the venotomy site (extravascular) and its location is verified using fluoroscopy prior to release. The clip is placed on the device shaft at the surface of the skin to hold the device in place during fluoroscopy.

Note, the principle of operation and the steps described below are identical to that of the previously approved device. Refer to the Instructions For Use document in **Attachment 3**.

## **2.1. Device Labeling**

A copy of the Instructions for Use (IFU) will be included with the devices. The Cardiva Mid-Bore Venous Vascular Closure System (VVCS) labels contain the following information:

- Venous Vascular Closure System
- Lot number
- Expiration (use by) date
- For Investigational Use Only

### **3. Study Objective**

The objective of the trial is to demonstrate the safety and effectiveness of the Cardiva Mid-Bore Venous Vascular Closure System (VVCS) in sealing femoral venous access sites and providing reduced times to ambulation (TTA) compared with manual compression at the completion of catheter-based procedures utilizing 6 – 12 Fr inner diameter procedural sheaths, with single or multiple access sites. This study will be considered a success from a statistical perspective if it meets both the Cardiva Mid-Bore VVCS superiority goal for the primary effectiveness analysis and the non-inferiority goal for the primary safety analysis as stated in Section 8.

### **4. Study Design**

#### **4.1. Overview**

This is a multi-center, randomized, controlled clinical trial to evaluate the safety and efficacy of the Cardiva Mid-Bore Venous Vascular Closure System (VVCS) compared to manual compression. Subjects will be randomly assigned in a 1:1 scheme to vascular closure with the VVCS or manual compression following percutaneous venous access for catheter-based procedures. Measures of safety and efficacy will be assessed through hospital discharge and 30 (+/- 7) days post-procedure.

#### **4.2. Sample Size**

204 subjects will be randomized in this trial in a 1:1 ratio, with randomization stratified by the number of femoral venous access sites (i.e., 3 v. 4). A total of 25 subjects each from the control and treatment arms will be enrolled in an ultrasound sub-study. In addition, up to 60 roll-in subjects may be enrolled.

#### **4.3. Investigational Sites**

This trial will be conducted at up to 20 clinical sites in the United States, with a minimum of 8 sites, enrolling subjects. Each site may enroll up to 25% of the pivotal subjects.

## 5. Study Population

### 5.1. Selection Criteria

The following pages outline the specific inclusion and exclusion criteria for the study. Before the study randomization, a patient must meet all of the inclusion and exclusion criteria.

#### 5.1.1. Pre-Operative Inclusion Criteria

Pre-Operative Inclusion Criteria	
All subjects are required to meet the following inclusion criteria in order to be considered eligible for participation in this trial:
 

1. 18 to 80 years of age;

2. Capable and willing to give informed consent;

3. Acceptable candidate for an elective, non-emergent catheter-based procedure via the common femoral vein(s) using a 6 to 12 Fr inner diameter introducer sheath, with a minimum of 3 and a maximum of 4 femoral venous access sites, and a maximum of 2 access sites/leg;

4. Able and willing to complete a 30 day +/- 7 days follow-up visit;

5. Acceptable candidate for emergent vascular surgery, and/or manual compression of the venous access sites;

6. A total of 50 subjects willing to undergo ultrasound evaluation at the 30 day +/- 7 day visit at select sites.

7. Anticipated prolonged bedrest (5 hours or longer) and / or overnight stay.

-----------------------------------------	----------------------------------------------------------------------------------------------------------------------------------------------------------------------------------------------------------------------------------------------------------------------------------------------------------------------------------------------------------------------------------------------------------------------------------------------------------------------------------------------------------------------------------------------------------------------------------------------------------------------------------------------------------------------------------------------------------------------------------------------------------------------------------------------------------------------------------------------------------------------------------------------------------------------------------------------------------------------------------------

## 5.1.2. Pre-Operative Exclusion Criteria

Pre-Operative Exclusion Criteria	
Subjects will be excluded from participating in this study if they meet any of the following criteria prior to initiation of the index procedure:
 
 
1. Advanced refusal of blood transfusion, if it should become necessary;
 
2. Active systemic infection, or cutaneous infection or inflammation in the vicinity of the groin;
 
3. Pre-existing immunodeficiency disorder and/or chronic use of high dose systemic steroids;
 
4. Known history of bleeding diathesis, coagulopathy, hypercoagulability, or current platelet count < 100,000 cells/mm^3;
 
5. Severe co-existing morbidities, with a life expectancy of less than 12 months;
 
6. Currently involved in any other investigational clinical trial that may interfere with the outcomes of this study, in the opinion of the Investigator;
 
7. Femoral arteriotomy in either limb with any of the following conditions:             
 
a. access within < 10 days
 
b. any residual hematoma, significant bruising, or known associated vascular complications
 
c. use of a vascular closure device within the previous 30 days;
 
 
 
8. Femoral venotomy in either limb with any of the following conditions:             
 
a. access within < 10 days
 
b. any residual hematoma, significant bruising, or known associated vascular complications
 
b. use of a vascular closure device
 
 
 
9. Any planned procedure involving femoral arterial or venous access in either limb within the next 30 days or prior to study exit;
 
10. Any history of deep vein thrombosis, pulmonary embolism or thrombophlebitis;
 
11. Significant anemia with a hemoglobin level less than 10 g/dL or a hematocrit less than 30%;
 
12. Renal insufficiency (i.e., serum creatinine of > 2.5 mg/dl);
 
13. Females who are pregnant, planning to become pregnant within 3 months of the procedure, or who are lactating;
 
14. Extreme morbid obesity (BMI greater than 45 kg/m^2) or underweight (BMI less than 20 kg/m^2);
 
15. Unable to routinely walk at least 20 feet without assistance;
 
16. Known allergy/adverse reaction to bovine derivatives;
 
17. Administration of low molecular weight heparin (LMWH) within 8 hours before or after the procedure;
 
18. Planned procedures or concomitant condition(s) that may extend ambulation attempts beyond 2-3 hours, and/or hospitalization time (e.g., staged procedure, serious co-morbidity), in the opinion of the Investigator.
 

-----------------------------------------	-------------------------------------------------------------------------------------------------------------------------------------------------------------------------------------------------------------------------------------------------------------------------------------------------------------------------------------------------------------------------------------------------------------------------------------------------------------------------------------------------------------------------------------------------------------------------------------------------------------------------------------------------------------------------------------------------------------------------------------------------------------------------------------------------------------------------------------------------------------------------------------------------------------------------------------------------------------------------------------------------------------------------------------------------------------------------------------------------------------------------------------------------------------------------------------------------------------------------------------------------------------------------------------------------------------------------------------------------------------------------------------------------------------------------------------------------------------------------------------------------------------------------------------------------------------------------------------------------------------------------------------------------------------------------------------------------------------------------------------------------------------------------------------------------------------------------------------------------------------------------------------------------------------------------------------------------------------------------------------------------------------------------------------------------------------------------------------------------------------------------------------------------------------------------------------------------------------------------------------------------------------------------------------------------------------------------------------------------------------------------------------------------------------------------------------------------------------------------------------------------------------------------------------------------------------------------------------------------------------------------------------------------------------------------------------------------------------------------------------------------------------------------------------------------------------

### 5.1.3. Intra-Operative Exclusion Criteria

Intra-Operative Exclusion Criteria	
Subjects will be excluded from participating in this study if any of the following exclusion criteria occur during the index procedure:
 
General Intra-op Exclusion Criteria:
 
 
5. Any attempt at femoral arterial access during the procedure;
 
6. Any procedural complications that may extend routine recovery, ambulation and discharge times;
 
7. If the physician deems that a different method should be used to achieve hemostasis of the venous access sites, or that the subject should not attempt ambulation according to the protocol requirements;
 
8. ALL venous access sites must comply with the following exclusion criteria immediately prior to randomization:             
 
d. Difficult insertion of procedural sheath or needle stick problems at the onset of the procedure (e.g., multiple stick attempts, accidental arterial stick with hematoma, "back wall stick", etc.) in any of the study veins;
 
e. A procedural sheath < 6 Fr or > 12 Fr in inner diameter is present at time of closure;
 
f. A procedural sheath > 12 Fr inner diameter at any time during the procedure.
 
d. Venous access site location is noted to be "high", above the inguinal ligament (cephalad to lower half of the femoral head or the inferior epigastric vein origin from the external iliac vein);
 
e. Intra-procedural bleeding around sheath, or suspected intraluminal thrombus, hematoma, pseudoaneurysm, or AV fistula;
 
f. Length of the tissue tract, the distance between the anterior venous wall and skin, is estimated to be less than 2.5 cm.
 
 
 

-------------------------------------------	------------------------------------------------------------------------------------------------------------------------------------------------------------------------------------------------------------------------------------------------------------------------------------------------------------------------------------------------------------------------------------------------------------------------------------------------------------------------------------------------------------------------------------------------------------------------------------------------------------------------------------------------------------------------------------------------------------------------------------------------------------------------------------------------------------------------------------------------------------------------------------------------------------------------------------------------------------------------------------------------------------------------------------------------------------------------------------------------------------------------------------------------------------------------------------------------------------------------------------------------------------------------------------------------------------------------------------------------------------------------------------------------------------------------------------------------------------------------------------------------------------------------------------------------------------------------------------------------------------------------------------------------------------------------------------------------------------------------------------------------------------------------

## 5.2. *Withdrawal of Subjects*

While study withdrawal is discouraged, subjects may withdraw from the study at any time, with or without reason and without prejudice to further treatment. In all cases of withdrawal, the reason(s) for withdrawal (if given) will be recorded upon study termination. In addition, the Investigator may withdraw the subject for any other reason determined by the Investigator to be in the best interest of the subject.

Once randomization is performed, subjects are considered enrolled and must have all peri-procedural data collected regardless of what treatment they receive after randomization, according to the Intent to Treat Principle for analyses of effectiveness.

Subjects who are randomized to VVCS and then never have the device inserted for any reason may be withdrawn after Discharge, since the safety analyses are based on subjects who receive

any part of the assigned treatment. All peri-procedural data must be collected for these subjects for effectiveness analyses.

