#### 7.4.4. Intra-Operative Randomization

At the end of the catheter-based procedure, with the procedural sheaths in place and under fluoroscopic visualization, an injection of contrast will be made to assess sheath placement and the anatomy of all venous access sites to verify the intra-operative eligibility criteria prior to randomization. These images should be saved and printed/stored with the subject's study records for monitoring purposes.

- Each venous access site must meet all intra-procedural access site-specific criteria for the subject to be eligible.

Once it has been determined that the subject does not meet any of the general intra-operative exclusion criteria, and that none of the venous access sites meet the specific access site exclusion criteria (i.e., all venous access sites must meet all study criteria for the subject to be eligible), then the subject is eligible for randomization.

- Once randomized, every access site will be closed according to the treatment assignment (i.e., either VVCS or manual compression).
- Study data will be captured for each access site, according to the instructions below.
- ***NOTE: Any subject that is randomized is considered to be enrolled, and all peri-procedural study data must be collected under the Intent to Treat principle regardless of deviations from the assigned treatment. For this reason, it is imperative that randomization is not performed until the case is complete and final eligibility criteria are confirmed.***
- ***If the subject is randomized to Mid-Bore VVCS and it is subsequently discovered that one or more of the access sites is not able to be closed (e.g., complication) apply manual compression to the affected access sites and close all eligible access sites using Mid-Bore VVCS. All study data will still be collected for each access site. See Section 4.2 Withdrawal of Subjects.***

At each investigational site, variable block randomizations will be performed separately by number of venotomy sites via EDC access at the conclusion of the index procedure, while the patient is on the table. Randomization will be stratified by 3 vs. 4 access sites, and there will be a 1:1 randomization ratio for Cardiva Mid-Bore VVCS vs. manual compression for access site closure. Refer to the Manual of Operations for instructions on how to randomize a subject.

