## **7.5. Follow-up at 30 (+/- 7) Days**

Subjects should be present for an in-person office visit  $30 \pm 7$  days following their index procedure. The subject should be queried regarding any complications they experienced after hospital discharge and the status of the access site wounds should be assessed. All subjects will be asked about any lower extremity nerve complaints in both lower limbs (i.e., symptoms, severity) that were not existing prior to the index procedure. These data will be captured in the Case Report Forms.

If a subject cannot attend an office visit for any reason, a telephone follow-up should be completed for safety assessment, however this will be documented as a protocol deviation and the subject's follow-up will be considered incomplete. These subjects will not be withdrawn.

At select sites, a subset of 25 subjects from each treatment arm will have an ultrasound exam of the bilateral femoral access sites performed and a digital image recorded for each limb.

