#### **9.1.2. Safety**

Safety analysis will be performed according to the actual treatment received. All subjects who receive any portion of the Cardiva VVCS device treatment will be analyzed as a VVCS patient; subjects who receive manual compression control treatment only as randomized will be analyzed as a manual compression patient.

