#### **9.1.3. Missing Data**

All efforts will be made to eliminate missing data for the primary effectiveness endpoint of TTA and primary safety endpoint of major access site closure complications. However, should missing data be non-trivial, the primary analyses will be based on complete cases with data and sensitivity analyses will be performed to assess robustness of the primary results. Multiple imputations strategy such as assuming missing at random and control based imputation will be employed for the primary effectiveness endpoint; worst case, best case and tipping point analyses will be performed for primary safety endpoint. Missing data for secondary endpoints will not be imputed by any method.

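### Subjects randomized to VVCS who never have the device inserted belong to neither safety group and may be withdrawn after discharge, so the primary safety comparison can lose subjects from one arm only

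*Combined protocol and SAP*

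**What the plan says.** Section 5.2 lets one group leave the study early: "Subjects who are randomized to VVCS and then never have the device inserted for any reason may be withdrawn after Discharge". The reason given is "since the safety analyses are based on subjects who receive" at least some of their assigned treatment. Peri-procedural data must still be collected from these subjects, for the effectiveness analyses. The control arm has no corresponding provision.

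Section 9.1.2 opens with an as-treated rule: "Safety analysis will be performed according to the actual treatment received". It then defines two groups. Anyone who receives any portion of the device counts as VVCS. For the control group, "subjects who receive manual compression control treatment only as randomized will be analyzed as a manual compression patient".

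Section 7.5 takes a stricter line with subjects who cannot attend the 30-day office visit. For them "a telephone follow-up should be completed for safety assessment", and "These subjects will not be withdrawn".

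For missing data, Section 9.1.3 says "worst case, best case and tipping point analyses will be performed for primary safety endpoint". It does not say whether these analyses cover subjects who are in neither safety group.

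**The concern.** A subject randomized to VVCS and closed entirely by manual compression would count as a control under the first sentence of Section 9.1.2. The definition of the control group then shuts that subject out, because compression was not the assigned treatment. Section 5.2 treats the exclusion as intended and uses it to justify ending follow-up at discharge.

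The exclusion happens after randomization and in one arm only. A control subject who receives any part of the device moves to the VVCS group and is not dropped. The comparison affected is open-label, expects few events, and is one of the two tests that decide trial success (Section 3).

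The scope is limited:

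- Subjects whose device was inserted but failed, and subjects converted at only some sites, stay in the VVCS group.
- In-hospital data are kept, so only status between discharge and day 30 can be lost.
- The primary time-to-ambulation analysis is unaffected.
- Procedure Success also needs 30-day status on all randomized subjects (Sections 8.2 and 9.1.1), but it is only described (Section 9.2.2.2).

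**Working it through.** **Inputs.** 204 subjects randomized 1:1 gives 102 per arm (Section 4.2). Three or four access sites with at most two per leg means both legs are used, so there are 102 × 2 = 204 limbs per arm. The assumed major complication rate is 2% per limb in both arms (Section 9.3), or 0.02 × 204 ≈ 4 events per arm. The test passes if the upper limit of the 2-sided 95% interval for VVCS minus manual compression is below 5%, using a bootstrap that resamples patients (Section 9.2.3). The number of never-inserted subjects, k, is not in the documents; 1 to 10 is assumed.

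**The plan's own figures.** With 204 limbs per arm at 2%, the Newcombe power is 0.877, against about 0.88 stated. With 2k limbs removed from the VVCS arm only, it is 0.878, 0.859, 0.863, 0.862 and 0.840 for k = 1, 2, 3, 5 and 10, so loss of power is not the main issue.

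The planned bootstrap was computed by exact enumeration, unstratified. If x events fall in x different patients out of n, the resampled count is Binomial(n, x/n) and the rate is that count divided by 2n. The limit is the 97.5th percentile of the difference. This reproduces Table 5, Sim 1: 6 v 4 events = 0.039, 6 v 2 = 0.049, 4 v 0 = 0.039, 6 v 0 = 0.054.

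**(1) How often would the two analyses disagree?** All limbs independent at 2% in both arms:

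| k | passes as written, fails as randomized | fails as written, passes as randomized |
|---|---|---|
| 1 | 0.2% | 0.0% |
| 3 | 0.2% | 3.8% |
| 5 | 0.4% | 3.3% |
| 10 | 0.6% | 3.1% |

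For k of 3 or more, most disagreements count against the device.

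**(2) Illustrations at the boundary.**

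- k = 5, one event among the five, control 4/204. As written, 7/194 gives 4.7% and passes. As randomized, 8/204 gives 5.4% and fails.
- k = 3, no event among the three, control 2/204. As written, 6/198 gives 5.05% and fails. As randomized, 6/204 gives 4.9% and passes.
- Counting these subjects as manual compression changes neither as-written result: 7/194 v 5/214 gives 4.7%, and 6/198 v 2/210 gives 5.05%.

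**(3) What lost status does to the Section 9.1.3 bounds at expected results.** Take 4 events in treated VVCS limbs and 4/204 in control.

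- As written: 2.5% (k = 1, 2), 2.6% (k = 3), 2.7% (k = 5).
- Best case, no events among the withdrawn: 4/204 gives 2.5%.
- Worst case, both limbs of each withdrawn subject: k = 1 gives 4.4% and passes; k = 2 gives 5.9% and fails.
- Worst case, one limb each: k = 3 gives 7/204, 4.4%, and passes; k = 4 gives 8/204, 5.4%, and fails.

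**The case against.** **The group should be small.** Section 7.4.4 says "it is imperative that randomization is not performed until the case is complete and final eligibility criteria are confirmed", subjects for whom the physician prefers another closure method are excluded beforehand, and withdrawal is optional. This stands, and it limits the severity.

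**The 3% to 4% figures are not evidence of selection.** Nearly all of that disagreement arises with no event among the never-inserted subjects (3.78 of 3.78 percentage points at k = 3, 3.30 of 3.30 at k = 5, 3.06 of 3.12 at k = 10). It comes from a smaller denominator acting on a discrete limit. This also stands; the figures show direction and fragility, not favour to the device.

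**A worst-case bound that fails is normal with rare events.** Failure at k = 2 needs a major complication attributed to closure in all four limbs, and a tipping-point analysis is also planned. That is fair. But no bound can recover a status that was never collected, and a 30-day contact would normally supply it.

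**Other sections keep some follow-up.** Section 13.1 monitors adverse events from randomization to the one-month visit and follows unresolved serious events. Section 7.6 delays exit while a condition needs follow-up. These protect events that begin in hospital. They do not capture a new event after a permitted withdrawal, and the Section 13.1 monitoring period itself conflicts with Section 5.2.

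**The asymmetry is partly structural.** Manual compression is the fallback for failed closure, so a mirror-image control group hardly exists. The endpoint also counts complications attributed to the closure method (Section 8.3), so charging compression complications to an unused device is not a natural primary analysis. This is a good reason to keep the as-treated primary and add the as-randomized analysis only as sensitivity. It is not a reason to stop follow-up.

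**Conclusion.** The concern holds. Section 9.1.2 leaves never-inserted VVCS subjects without a safety group, and Section 5.2 relies on that to let them leave before the 30-day endpoint. The result is an avoidable, one-sided loss of subjects after randomization in the primary safety comparison.

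Its likely size is small. A false pass relative to the as-randomized analysis has probability of at most 0.6% across the values of k examined, the bias has no fixed direction, and a changed conclusion needs results near the 5% boundary. The clearer cost is that as few as two withdrawals could make the prespecified worst-case analysis fail at otherwise expected results. These figures assume 2% per limb in both arms, independent limbs in the disagreement probabilities, an unstratified bootstrap, and k between 1 and 10. The change should be made, but the trial does not depend on it.

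**What to change.** 1. Delete the Section 5.2 permission. Require 30-day follow-up of every randomized subject, with the Section 7.5 telephone contact as fallback. The subject's own right to withdraw is unchanged.
2. Add the same patient-level bootstrap on all randomized subjects as assigned, as a sensitivity analysis beside the as-treated primary. Report how many VVCS subjects never had a device inserted, and why.
3. State in Section 9.1.2 which as-treated group these subjects join. Manual compression follows from that section's first sentence. This closes the wording gap but does not change the illustrations.
4. State that the Section 9.1.3 safety sensitivity analyses cover these subjects.

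Items 1 and 2 are the substance; the fix does not depend on the grouping chosen in item 3. The cost is protocol and SAP wording, a visit or telephone call for a few subjects who already agreed to the 30-day visit at entry, and one extra analysis. It should be done before any such withdrawal, because lost status may not be recoverable.
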